Administration Of Calcium Gluconate for The Reduction of Blood Loss During Elective Cesarean Delivery

INTRODUCTION

Postpartum hemorrhage (PPH) is the leading cause of death related to pregnancy, reported as 5% of all deliveries and assumed to be underestimated [1]. Known risk factors include uterine atony, genital tract trauma, retained placental tissue and more [2]. PPH can lead to blood transfusion, disseminated intravascular coagulation (DIC), hysterectomy, or death [2]The prophylactic administration of uterotonic agents as part of an active management of the third stage of labor has been proven to reduce rates of PPH [3]. However, even with these treatments, PPH rate is still relatively high, and puts women at risk of heavy bleeding and death. In addition, PPH is a risk factor for postpartum complications such as venous thromboembolic disease [4].

Calcium is a divalent cation found both intracellular and extracellular. It is a key component in the coagulation cascade and known as factor IV. It has a role in platelet activation, and it is an important co-factor for the activation of factors II and X [5]. K. M. Ho et al. had proven a concentration-dependent effect of hypocalcemia on in vitro clot strength in patients at risk of bleeding [6]. Calcium gluconate is the calcium salt of gluconic acid, and it has a relatively strong safety profile.

Hypocalcemia is a poor prognostic factor in actively bleeding patients. In trauma, the term "the trauma triad of death", describing the combination of hypothermia, acidosis, and coagulopathy as a vicious cycle that can lead to patient death eventually, has been changed to "the diamond of death" or "the lethal diamond", including hypocalcemia in the positive feedback loop of patient deterioration[7]–[9], emphasizing the need to monitor calcium levels when treating trauma patients with hemorrhagic shock. This mechanism doesn't apply only to trauma patients but to every patient that suffers from significant bleeding [10], [11]

Calcium also has a positive inotropic effect both on skeletal muscle and smooth muscle. The inotropic effect doesn't skip the myometrium, and it is well-established that hypocalcemia can impair myometrial contractility [12], [13]. As so, calcium channel blockers are prescribed as a tocolytic drug and calcium gluconate should be considered as adjuvant therapy for treating PPH duo to atony, in case of prolonged tocolytic or magnesium sulfate use prior to delivery [14]. Studies have already shown an association between low ionized calcium levels and the risk for severe bleeding. In one study, the rate of hypocalcemia was 10.6% in patients with non-severe PPH and 51.5% in patients with severe PPH [15]. Furthermore, in a pilot randomized controlled trial of patients with risk factors for uterine atony, calcium was shown to reduce uterine atony compared to placebo [16]. However, current studies have small sample size and are limited to a high-risk population. Although it is acknowledged that hypocalcemia combined with acidosis and hypothermia contribute to worsening coagulopathy and increased morbidity in PPH [2], there are no recommendations in current guidelines for monitoring calcium levels or prescribing calcium as a prophylactic measure for the third stage of labor [15], despite atony and coagulopathy being significant causes of PPH.

Co-administration of calcium and oxytocin was examined in previous study, and there were no changes in maternal hemodynamics [17].

HYPOTHESIS

Administration of Calcium Gluconate at the third stage of elective Cesarean delivery will decrease the rates of blood loss during and after the surgery by reducing the rates of uterine atony and development of coagulopathy, thus has the potential of reducing the incidence of PPH and its complications without severe side effects.

RESEARCH QUESTIONS

Primary research question

Population (P), Intervention (I), Comparison (C), Outcome (O)

- P: All women undergoing elective cesarean delivery.
- I: Administration of Calcium Gluconate 10% IV following umbilical cord clamping.
- C: Administration of normal saline 0.9% IV following umbilical cord clamping.
- O: Decreased mean hemoglobin drop after cesarean delivery.

Outcome measures

Primary outcome:

.1 Decreased mean hemoglobin drop after cesarean delivery at the Calcium gluconate arm, compared to the control arm.

Secondary outcome:

- 1. The rate of women with a decrease of hemoglobin levels of 2 gr/dl or more.
- 2. The need for additional therapy for the management of PPH
- 3. Receipt of blood products.
- 4. Patients treated with intravenous ferrous (iron).
- 5. The estimated blood loss during the surgery.
- 6. Hospitalization length of stay.
- 7. Duration of cesarean delivery.
- 8. A composite of adverse maternal outcomes including at least one of the following: admission to intensive care unit (NICU), the need for a surgical treatment for uncontrolled PPH, massive blood transfusion (defined as transfusion of ≥10 units red blood cells (RBCs) in 24 hours, disseminated intravascular coagulation (DIC), and death.
- 9. Endometritis or antibiotic treatment following CD.

PROPOSED TRIAL

Design: Multi Center (Rambam Health Care Campus, Soroka Medical Center), clusterrandomized, double-blind controlled trial.

Eligibility criteria for participants:

We plan to conduct a randomized control trial of all women undergoing elective cesarean delivery.

Inclusion criteria:

1. Gestational age of 35 weeks or more.

Exclusion criteria:

- 1. Age younger than 18 years old.
- 2. Patients treated with calcium channel blockers.
- 3. Chronic renal failure and hyperphosphatemia.
- 4. Sarcoidosis.
- 5. Hypocalcemia (ionized Ca<1 mmol/L) or hypercalcemia (ionized Ca> 1.3 mmol/L) before the surgery.
- 6. Any QT abnormalities as evident by ECG before Calcium Gluconate administrations or any known conduction abnormality.

Research arms and randomization:

After signing a consent form prior to the surgery (at the pre-operative assessment), At the third stage of labor, women who gave their consent to participate in the study will get either 10 ml of Calcium Gluconate 10% solution (containing 0.94 gr of calcium gluconate) diluted in 100 ml of normal saline IV or 110 ml of normal saline IV.

The solutions will be given in addition to Carbetocin (a long acting oxytocin analogue), in both arms.

We will use calcium gluconate during even-numbered months and normal saline during oddnumbered months, or vice versa, according to randomization that will be known to the primary researcher alone.

A blood sample will be drawn at the beginning of the surgery and sent for blood gas analysis, determining ionized calcium levels and coagulation profile. Women with hypocalcemia or hypercalcemia will be excluded from the trial. Only patients with normal calcium levels between 1.0-1.3 mmol/L will be included in this trial.

An ECG strip will be done prior to the surgery, making sure that the patient doesn't suffer from a QT segment abnormality.

All patients will be monitored with a 3 lead- ECG prior, during, and 2 hours following calcium administration. Patients with QT interval abnormalities will be excluded from the trial.

After the surgery, a blood sample will be drawn and sent to blood gas analysis (determining ionized calcium levels) and for coagulation profile. A complete blood count will be routinely taken for all women the next day. The hemoglobin level will be compared to the hemoglobin level prior to CD.

ANALYSIS PLAN

Binyamin Y et al. demonstrated an average blood loss of 1.05 g/dL in 1000 women who have had a cesarean delivery for different indications[17]. Assuming a reduction in blood loss of 30% attributed to both coagulative effect and uterotonic effect of Calcium, and calculating a dropout rate of 10%, a sample size of 1180 patients (590 in each arm) is needed to achieve power of 0.8 and p-value <0.05. We will use SPSS 28 (IBM inc.) for statistical analysis. Categorical variables will be compared using the chi-square test or fisher's exact test. Continuous variables will be compared using the student's t-test or Mann-Whiteny test. After testing for collinearity, confoundment and interaction, a multivariate model will be built to assess the effect of calcium supplementation on postpartum hemorrhage. Alpha < 0.05 is considered statistically significant.

References:

- C. Deneux-Tharaux, M.-P. Bonnet, and J. Tort, "[Epidemiology of post-partum haemorrhage].," J Gynecol Obstet Biol Reprod (Paris), vol. 43, no. 10, pp. 936–50, Dec. 2014, doi: 10.1016/j.jgyn.2014.09.023.
- [2] "Postpartum Hemorrhage ACOG PRACTICE BULLET IN Clinical Management Guidelines for Obstetrician-Gynecologists," 2017. [Online]. Available: http://www1.health.nsw.gov.au/pds/ActivePDSDocuments/
- [3] L. Sentilhes, F. Goffinet, C. Vayssière, and C. Deneux-Tharaux, "Comparison of postpartum haemorrhage guidelines: discrepancies underline our lack of knowledge," *BJOG*, vol. 124, no. 5, pp. 718–722, Apr. 2017, doi: 10.1111/1471-0528.14305.
- [4] L. Thurn, A. Wikman, and P. G. Lindqvist, "Postpartum blood transfusion and hemorrhage as independent risk factors for venous thromboembolism," *Thromb Res*, vol. 165, pp. 54–60, May 2018, doi: 10.1016/j.thromres.2018.03.002.

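### The hypothesis includes freedom from severe side effects, but no listed outcome is specific to calcium harm, and severe harm can show only inside a hemorrhage-dominated composite

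*Protocol*

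**What the plan says.** The Hypothesis section ends with a safety statement: "thus has the potential of reducing the incidence of PPH and its complications without severe side effects".

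Under Outcome measures, the primary outcome is "Decreased mean hemoglobin drop after cesarean delivery at the Calcium gluconate arm, compared to the control arm". Nine secondary outcomes follow. The one nearest to severe harm is number 8, which begins "A composite of adverse maternal outcomes including at least one of the following: admission to intensive care unit (NICU". It goes on to surgery for uncontrolled PPH and massive transfusion, and ends with "disseminated intravascular coagulation (DIC), and death". The composite is of maternal outcomes, so I read the abbreviation there as maternal intensive care.

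The section on research arms and randomization describes two relevant measurements:

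- "All patients will be monitored with a 3 lead- ECG prior, during, and 2 hours following calcium administration".
- "After the surgery, a blood sample will be drawn and sent to blood gas analysis (determining ionized calcium levels) and for coagulation profile".

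Neither is linked to a listed outcome. The Analysis Plan names general tests for categorical and continuous variables, and one multivariable model, which is for postpartum hemorrhage.

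**The concern.** The hypothesis joins a benefit with an absence of severe side effects, but the outcome list serves almost only the benefit. The protocol shows which risks it has in mind: it excludes women with ionized calcium above 1.3 mmol/L and those with QT or conduction abnormalities, and it monitors the ECG after dosing. None of these risks returns as an outcome.

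If the outcome list is followed as written, the safety half of the conclusion would rest on a composite that mostly counts consequences of bleeding. A favorable composite could then be read as evidence of safety when it mainly reflects efficacy. That matters for a drug given prophylactically to all eligible women having an elective cesarean.

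**Working it through.** **1. What each outcome can show about calcium harm**

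| Outcome | Subject | Specific to calcium harm? |
|---|---|---|
| Primary; secondary 1 | Hemoglobin drop | No |
| Secondary 2 to 5 | PPH therapy, blood products, iron, blood loss | No |
| Secondary 6, 7 | Length of stay, duration of surgery | No; stay is all-cause but indirect |
| Secondary 8 | ICU admission, surgery for PPH, massive transfusion, DIC, death | No; ICU admission and death are all-cause |
| Secondary 9 | Endometritis or antibiotics | No |

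**2. How the composite can mask harm**

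Suppose calcium lowers the rate of bleeding-related composite events by *b* and raises the rate of calcium-related ICU admission or death by *h*. If the two kinds of event rarely fall in the same woman, the between-arm difference in the composite is about *h* − *b*. Any harm with *h* no larger than *b* then gives a composite that looks neutral or favorable. An event that leads to neither ICU admission nor death contributes nothing to *h*.

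**3. What the planned size could show if harm were counted**

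No figure in the protocol bears directly on safety. The 1180 women were sized for the hemoglobin outcome, and I take 590 per arm as given. With the stated 10% dropout, 590 × 0.9 = 531 per arm.

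One-sided 95% upper bound after zero events, 1 − 0.05^(1/n):

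- n = 590: 0.51%
- n = 531: 0.56%

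Chance of at least one event in the calcium arm, 1 − (1 − p)^531, at assumed true rates:

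| True rate p | Chance of at least one event |
|---|---|
| 0.1% | 41% |
| 0.2% | 65% |
| 0.5% | 93% |
| 1% | 99.5% |

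Power for a between-arm difference δ, two-sided 5%, n = 531 per arm, with p̄ the mean of the two rates:

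Φ{[δ√n − 1.96√(2p̄(1 − p̄))] / √(p₁(1 − p₁) + p₂(1 − p₂))}

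For an assumed 1% versus 2% this is Φ{(0.2304 − 0.3369)/0.1718} = Φ(−0.62) = 27%. For 1% versus 3% it is 64%, and for 1% versus 4% it is 88%.

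So the trial can describe event rates with useful bounds, but it cannot reliably test for a difference in rare events.

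**4. The two statements on QT abnormality**

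Exclusion criterion 6 refers to an ECG before calcium is given. The later sentence that excludes women with QT abnormalities gives no time, and it directly follows the description of monitoring during and after administration. Applied after dosing, it would remove the women in whom a calcium effect might have appeared.

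**The case against.** Several points on the other side are sound.

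- **Some severe harm is counted.** A reader might infer that no outcome measures harm, or that the composite cannot detect calcium toxicity. The protocol does not support this. ICU admission and death in outcome 8 carry no cause, and the hypothesis speaks only of severe effects. Toxicity that leads to either would be counted and compared. What remains is the masking, and the loss of events short of ICU admission.
- **The collected data may be analyzed.** A reader might infer that the ECG and calcium data would go unused. The Analysis Plan does not restrict its general tests to listed outcomes, and the statistical analysis plan is not shown and may well tabulate safety. The list of outcomes, however, belongs to the protocol and is fixed there without them.
- **The safety wording is hedged.** It speaks of potential, and the primary research question makes no safety claim. This lowers the weight of the point. It does not remove the gap between the hypothesis and the outcomes.
- **1.3 mmol/L is an eligibility limit.** Exceeding it after receiving calcium is to be expected in some women and is not in itself a severe side effect.
- **Hemodynamic harm is not among the monitored risks.** A reader might infer that it is, but no exclusion or monitoring step concerns it, and no collection of blood pressure data is described. The point does not extend that far.
- **Post-dose QT may not be recorded.** An ECG strip is described only before surgery. Afterwards there is 3-lead monitoring, with no statement of what is written down. The fix therefore needs some recording as well as analysis.

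**Conclusion.** The point holds in a limited form. The protocol has no outcome specific to calcium harm. Severe harm is visible mainly through all-cause ICU admission and death, pooled with bleeding complications that should fall if calcium works. The primary efficacy analysis is unaffected; what is weakened is the safety half of the hypothesis. This is a worthwhile, inexpensive improvement and not a fatal flaw.

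Even after the fix, zero events would bound a severe-event rate only below about 0.5 to 0.6% per arm, and power for rare differences would be low (27% at an assumed 1% versus 2%). These figures treat women as independent. Allocation is by calendar month, so the between-arm comparison may carry less information than they suggest. The event rates are assumptions, because the protocol gives none.

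**What to change.** Add a safety outcome to the protocol, compared between arms and reported separately from outcome 8:

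1. Post-operative ionized calcium, as change from the start-of-surgery value and as the proportion above the protocol's own 1.3 mmol/L eligibility limit. Label the latter as descriptive and not as a harm threshold.
2. Any new rhythm, conduction or QT abnormality seen on the ECG monitoring during administration and for 2 hours after it, with the same window in both arms, counted from the study infusion. State what is recorded from the monitor.
3. ICU admission and death, each shown by arm in addition to their place in the composite.

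Report event rates with 95% confidence intervals, and limit any conclusion about severe side effects to these outcomes and bounds.

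Reconcile the untimed sentence on QT abnormalities with exclusion criterion 6, and state that women with an abnormality first seen after dosing remain in the between-arm comparison.

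The cost is protocol wording, a few case-report-form fields with the related data entry, and more outcomes to report. No extra sample, procedure or participant is needed, and the sample size does not change.

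### The fixed even/odd month rule keeps each named month in one arm every year; if one draw serves both hospitals, irregular month effects cannot be separated from calcium

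*Protocol*

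**What the plan says.** The Design line under PROPOSED TRIAL reads "Design: Multi Center (Rambam Health Care Campus, Soroka Medical Center), clusterrandomized, double-blind controlled trial". Under Research arms and randomization the allocation is: "We will use calcium gluconate during even-numbered months and normal saline during oddnumbered months, or vice versa, according to randomization". That is one rule, with one choice of direction, for a trial at two hospitals. The section does not say whether the direction is drawn once or separately for each hospital. It describes no opposite parity, no reversal after a year and no random order within pairs of months.

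The ANALYSIS PLAN takes its control value from a study that "demonstrated an average blood loss of 1.05 g/dL in 1000 women" and continues: "Assuming a reduction in blood loss of 30% attributed to both coagulative effect and uterotonic effect of Calcium". With 10% dropout it concludes that "a sample size of 1180 patients (590 in each arm) is needed" for power 0.8 at the 0.05 level. It gives no standard deviation, accrual period or rule for closing recruitment. Continuous outcomes are to be compared by t-test or Mann-Whitney test, with a multivariable model whose covariates are not listed.

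**The concern.** The point is about the calendar, not about concealment or the choice of test. A named month never changes parity, so a second or third year repeats the same pairing of months with arms. If both hospitals follow the same parity, no woman on calcium has a concurrent control in her own month. The primary comparison is then six named months against the other six.

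Anything that makes particular months differ irregularly and recurs each year (staff intake, holiday staffing, case mix) adds to the estimated calcium effect. More women or more years shrink the sampling error but not this component. The protocol itself fixes this: once treatment is determined by calendar month, a later analysis plan cannot restore the missing within-month contrast.

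**Working it through.** **Inputs from the protocol.** Control mean drop 1.05 g/dL, reduction 30%, dropout 10%, 590 per arm, power 0.8, alpha 0.05 (taken as two-sided).

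**1. The plan's own figures.**
- Target effect: 0.30 × 1.05 = 0.315 g/dL.
- Analysed per arm: 590 × 0.9 = 531.
- The 590 cannot be reproduced directly because no SD is given. Solving for it: SD = 0.315 × √(531/2) / (1.960 + 0.842) ≈ 1.83 g/dL.
- An assumed SD of 1.0 would need only 159 per arm, or 177 after dropout.
- Sampling standard error, SD × √(2/531): 0.061 g/dL at SD 1.0 and 0.112 at SD 1.83. Both are carried forward.

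**2. Parity.** Month number m and month number m + 12 have the same parity, whether months are counted by the calendar or from study start. Within a hospital, each named month is therefore always in one arm.

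**3. Can treatment be separated from month?** Take 12 month indicators, one site indicator and year indicators, then add the treatment column.

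| Years | Shared parity: rank without / with treatment | Opposite parity: rank without / with treatment |
|---|---|---|
| 1 | 13 / 13 | 13 / 14 |
| 5 | 17 / 17 | 17 / 18 |
| 10 | 22 / 22 | 22 / 23 |

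Under shared parity, 0 of 12 named months contain both arms, and treatment is an exact combination of the month indicators however long the trial runs. Under opposite parity all 12 contain both arms and the calcium effect is estimable.

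**4. What cancels and what does not.** Over whole years with equal monthly enrolment, seasonal waves with one to five cycles a year give exactly zero even-minus-odd difference. Only the component that alternates from month to month gets through. Over part-years some smooth season remains: per unit amplitude of an annual wave, at most about 0.35 at 6 months, 0.10 at 10 months and 0.12 at 18 months. A lasting change in practice runs through all later months and so reaches both arms. A recurring shift of 0.5 g/dL in one named month moves the contrast by 0.5/6 = 0.083 g/dL every year. A shock confined to one month falls on one arm, but is diluted as accrual lengthens.

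**5. Size.** The protocol gives no figure for month effects. Assume 12 independent recurring effects with SD τ. The difference between two means of six has SD √(2τ²/6), for any number of years. The last two columns give the two-sided rejection rate under no calcium effect when the test ignores this component, using total SD √(SE² + 2τ²/6).

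| τ (g/dL, assumed) | SD of contrast | 1.96 × SD | Share of 0.315 | Rejection rate, SD 1.0 | Rejection rate, SD 1.83 |
|---|---|---|---|---|---|
| 0.05 | 0.029 | 0.057 | 18% | 8% | 6% |
| 0.1 | 0.058 | 0.113 | 36% | 15% | 8% |
| 0.2 | 0.115 | 0.226 | 72% | 36% | 17% |

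**6. Sensitivity to independence.** If neighbouring months correlate at 0.5, decaying by powers around the year, the variance is multiplied by 1 + 2(−0.5 + 0.25 − 0.125 + 0.0625 − 0.03125) + 0.0156 ≈ 0.33. The SDs fall by a factor of about 0.57, to roughly 0.017, 0.033 and 0.066 g/dL.

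**7. After the change.** With opposite parity and enrolment shares w₁ and w₂, a month effect common to both hospitals enters the crude comparison multiplied by |w₁ − w₂|: 0 with equal enrolment, 0.2 at a 60/40 split. With site and calendar month in the model it drops out.

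**The case against.** **Shared parity is inferred.** A reader might take it as settled that both hospitals give the same solution in the same month. The protocol does not say so. One rule with one choice of direction reads most naturally as a single draw, but separate draws are possible and would give shared parity half the time. This objection stands, so the conclusion is conditional. The first half, that a named month never changes arm within a hospital, needs no such condition.

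**Monthly alternation is a good balancer.** A reader might infer that ordinary seasons, or a new product or practice, would bias the result. Step 4 shows that they largely do not. Only irregular month-specific effects and shocks lasting about a month are at issue.

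**The size rests on assumed inputs.** This also stands. τ has no source in the protocol, and 0.2 g/dL would be 19% of the whole mean drop (0.2/1.05). The upper rows of the table are not estimates. An outcome SD of 1.0 does not fit 590 per arm, and at the implied 1.83 the month component is smaller relative to sampling error.

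**An analysis can still help.** It is tempting to say that no analysis can separate months from calcium. That is true only for unrestricted month effects. Smooth calendar terms, measured staffing or case-mix covariates, or a random month effect that widens the interval all remain open. None of them supplies the missing concurrent control.

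**Recruitment may not close by arm count.** A reader might infer from 590 per arm that the slower arm would fill last, in months without a counterpart. The protocol gives 590 as the size needed for power and states no closing rule, so this is a gap to close and not a described procedure.

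**Conclusion.** The point holds as a narrow, conditional design weakness that is cheap to remove. The even/odd rule ties each named month to one arm within a hospital for the whole trial. If the single draw covers both hospitals, treatment is an exact function of calendar month. Irregular recurring month effects and month-long shocks are then confounded with calcium and cannot be removed by adjusting for month.

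The size is unknown. Under the assumptions in step 5 it ranges from minor (τ = 0.05) to comparable with the sampling error or larger (τ = 0.2), and it is smaller if neighbouring months resemble each other. The documents do not show that the result would be biased, only that the design gives no protection against this component.

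**What to change.** Amend the randomization paragraph to state that:
- the two hospitals run opposite parity, with the hospital that starts on calcium chosen at random;
- parity is reversed at both hospitals after 12 months if accrual runs longer;
- recruitment at each hospital ends on a complete calcium/saline month pair.

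In the ANALYSIS PLAN, estimate the effect with site and calendar month in the model.

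The cost is one paragraph, a changed supply calendar, and a final count that may differ from 1180 by part of a month. No extra staff, procedures or patients are needed by design. One limit remains: month effects specific to one hospital stay confounded within that hospital if accrual lasts less than a year, because the reversal then never takes place.

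### Only the month parity is randomised, so the code holder knows every future arm and one identified month reveals all others at that site

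*Protocol*

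**What the plan says.** The Proposed Trial section gives the design as "Design: Multi Center (Rambam Health Care Campus, Soroka Medical Center), clusterrandomized, double-blind controlled trial". Under Research arms and randomization, one arm is assigned to all even calendar months and the other to all odd ones: "normal saline during oddnumbered months, or vice versa, according to randomization that will be known to the primary researcher alone".

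Enrolment is individual. Treatment follows "After signing a consent form prior to the surgery (at the pre-operative assessment"), and the operation is elective.

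Two exclusions are applied when the arm for that date is already fixed:
- Ionized calcium, from a sample taken as surgery begins: "Women with hypocalcemia or hypercalcemia will be excluded from the trial". It has numeric limits (1.0 and 1.3 mmol/L).
- QT and conduction findings: "Any QT abnormalities as evident by ECG before Calcium Gluconate administrations or any known conduction abnormality", based on a tracing before the operation ("An ECG strip will be done prior to the surgery"). No numeric limit is given.

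For masking, the infusion volumes match: 10 ml of calcium gluconate "diluted in 100 ml of normal saline IV or 110 ml of normal saline IV". The Protocol does not say who prepares the bags, who sees the post-operative ionized calcium result, or whether the primary researcher recruits, treats or assesses outcomes.

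**The concern.** Randomisation protects a comparison only if those who schedule, consent and exclude women cannot foresee the arm. Here a single binary draw is followed by fixed alternation, and the arm depends on nothing but the date of a planned operation. Someone who knows the schedule could, deliberately or not, influence which women are booked, approached or excluded in each kind of month.

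The primary outcome is a hemoglobin change from a routine blood count, so judgement in measuring it is a minor worry. Selection of women by arm is its main exposure. Selection cannot be reliably undone in analysis: women who were never booked or approached leave no data, and the multivariate model in the Analysis Plan can adjust only for what was measured.

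If a month becomes known, masking is also not secured for outcomes that clinicians decide or estimate: additional therapy for hemorrhage, transfusion, intravenous iron, "The estimated blood loss during the surgery", length of stay and antibiotic treatment.

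**Working it through.** The Protocol gives no figure for predictability, so there is none to reproduce. The calculation counts arms that could be known under the stated rule and under alternatives.

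**Inputs**
- 1180 women (Analysis Plan) and two sites (Proposed Trial).
- Assumed, because the Protocol does not state them: recruitment of 6, 12 or 24 months, two sites of equal size, even recruitment over time.

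**Possible schedules.** One draw for the trial gives 2^1 = 2. One draw per site gives 2^2 = 4. Neither depends on trial length.

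**One leaked month.** Under parity, every other month at that site is then known with certainty. With 12 months in random balanced order (6 per arm), the best guess for any other month is the opposite arm, correct with probability 6/11 = 55%. With 24 months it is 12/23 = 52%. Pure guessing gives 50%.

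**A. Arms known before the period starts** (matters for scheduling and consent).

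Parity, first month identified at each site, share = (T − 1)/T:
- 6 months: 5/6 = 83%, about 983 women
- 12 months: 11/12 = 92%, about 1082
- 24 months: 23/24 = 96%, about 1131

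Random balanced order of n = 2m periods per site, under the harsh assumption that every earlier period is known. A period is determined in advance only once one arm has been used up. The expected number of such periods is 2m/(m + 1):
- Months, n = 6, 12, 24: 1.50, 1.71, 1.85 periods, or 25.0%, 14.3%, 7.7% (at 12 months about 169 women)
- Weeks, n = 26, 52, 104: 1.86, 1.93, 1.96 periods, or 7.1%, 3.7%, 1.9% (at 52 weeks about 44 women)

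A simulation at n = 6, 12, 24, 26 and 52 gave 24.9%, 14.2%, 7.7%, 7.2% and 3.7%.

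**B. Arms known when a woman is treated**, if the first woman in every site-period reveals the arm (matters for clinician-decided outcomes).
- Parity: only the first woman at each site is unknown, 1178/1180 = 99.8%.
- Random periods: 1 − 2n/1180. Months: 99.0%, 98.0%, 95.9%. Weeks: 95.6%, 91.2%, 82.4% (1128, 1076, 972 women). This ignores the one or two forced periods at the end of each site's list, which is negligible.

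**Stock switches per site.** Parity over 12 months: 11. Random balanced order: n − 1 adjacent pairs, each differing with probability (n/2)/(n − 1), so n/2 expected. That is 6 for 12 months and 26 for 52 weeks.

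**Calendar balance.** Of the C(12,6) = 924 balanced orders of 12 months, C(6,3)² = 400 (43%) split the first six months 3:3. The rest (57%) split 4:2 or worse, and 74 (8%) split 5:1 or worse. Alternation always gives 3:3.

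**The case against.** The strongest reply is that no breach is shown. The code is restricted to one person, the trial is labelled double-blind and the volumes match. The documents give no expected calcium rise, so the post-operative result cannot be said to reveal the arm. Nor do they say how freely an operation can move between months. All of this stands: the finding is weak concealment, not broken concealment.

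Second, the holder of any pre-generated list knows every future arm, so the primary researcher's knowledge does not come from parity. That is right. There are two faults, each with its own remedy: an unpredictable order for one, an independent holder for the other. What the Protocol leaves unsaid about roles is not itself the fault; the rule and the named holder are.

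Third, the percentages rest on an assumed duration and assumed leaks, and they do not measure harm. This also stands. The defect itself needs neither assumption.

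Fourth, random months hardly change scenario B (99.8% to between 99% and 96%). That is true if every period is unmasked. It does not answer the case of a single leak, which exposes the whole schedule at that site under parity but essentially only its own period under a random order.

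Fifth, alternation guarantees calendar balance and a random order does not. This is a real cost, quantified above. Randomising within pairs of months would keep the balance and allows 2^6 = 64 schedules over 12 months, but the second month of each pair is then known from the first.

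**Conclusion.** The concern holds. The Protocol fixes an allocation rule with two possible schedules (four if drawn by site) and names the primary researcher as sole holder of the code, without separating that role from recruitment, care or assessment. Concealment then depends on that person's discretion and on no month ever being identified.

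In size, all 1180 arms are known in advance to one person. For anyone else none is known at first, rising to 83% to 96% known ahead of time if the first month is identified at each site, given the assumed 6 to 24 months and even recruitment. The resulting bias in the hemoglobin comparison cannot be derived from the Protocol. The rule should be changed because the exposure is avoidable at low cost and cannot be reliably repaired in analysis.

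**What to change.** Replace the parity rule with a computer-generated, unpredictable list held by pharmacy or by a statistician with no role in recruitment, care or outcome assessment, and state who prepares the bags.

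- **Smallest change:** keep whole periods, but randomise their order independently at each site without fixed pairs. Months are the least work; weeks are less predictable.
- **Stronger option, where coded 110 ml bags can be prepared for each woman:** randomise individual women, stratified by site. One woman's arm then does not give the next, which also removes predictability within a period.

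**Cost.** A protocol amendment, a new list and an independent holder. Random months need no extra stock switches on average; random weeks need more. With either, the rest of an identified period stays predictable and calendar time is balanced less tightly. Individual randomisation changes the stated cluster design and requires a bag for each woman at two sites. It need not raise the 1180, since the Analysis Plan builds in only 10% dropout and no cluster term.
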